3.3 Expected Toxicities

There are a few specific toxicities that are of concern in the irradiation of tumors in the liver. The first concerns the overall maintenance of good hepatic function. From the data in the literature^{4,5}, this appears to be strongly related to the amount of liver in the radiation field treated to moderate dose. The data from liver resection surgery has shown that with a proliferative response, the liver can regenerate itself after removal of ½ or more of the liver. This regeneration will likely not occur if the remaining liver has received a significant amount of radiation, although the dose that would prevent regeneration is not known.

Secondly, the primary biliary radicals could be damaged by the radiation. This would likely be a late response, although initial edema could produce an acute temporary obstruction that would likely be minimized by the use of steroids. Long term, fibrosis could occur producing biliary obstruction.

Third, there can be vascular injury producing a veno-occlusive picture with hepatomegaly and other signs of liver failure that can occur about 3 months after irradiation. In addition, as the liver is in close proximity to multiple normal structures, the tolerance of these structures (liver, lung, esophagus, duodenum) must also be considered as ulceration and necrosis could occur if those structures are irradiated to high dose. Toxicity from structures distant to the radiation beam is very unlikely. Doses to all the above mentioned normal tissues can be calculated during the planning phase of the therapy to allow us to estimate high-risk sites.

These toxicities described above are primarily captured in the CTCAE, Version 3.0 formulation as hepatic and biliary tract related, and they will be measured accordingly. We would not expect toxicities in other organs other than liver, stomach, bowel, or lung. However, all toxicities that are not clearly ascribable to other unrelated causes or to tumor progression will count for the toxicity evaluation.

Dose modifications for individual patients will be based on dosimetric information as described above. As all treatments will be delivered over approximately one to two weeks, there is no expectation that acute toxicities will occur. However, acute toxicities (defined as within one week of the delivery of the radiation therapy) that are possible include toxicity related to the gastrointestinal, cardiac and pulmonary systems. Any acute Grade 3 or greater toxicity as defined by the CTCAE, Version 3.0 will be assessed regarding the organ of origin and the dose-volume relationship in that organ evaluated.

4.0 PATIENT ELIGIBILITY

Each patient must meet all of the following eligibility criteria to be enrolled in the study:

4.1 Inclusion Criteria

1. Hepatocellular carcinoma (as defined by biopsy or alpha-fetoprotein (AFP) greater than 1000ng/dL with appropriate imaging) or liver metastases from colorectal cancer or other tumor (as defined by biopsy or elevated CEA or a positive PET scan in conjunction with a mass on CT or MRI in a patient with previously resected cancer). Patients with at least one measurable liver lesion and no more than 3 lesions are eligible if they meet all other eligibility criteria including the dose constraints on the composite plan.
2. ECOG Performance Status 0-1.
3. Patients who are not candidates for definitive surgical resection because of tumor location, hepatic function, or other medical or personal reasons.
4. Patients with HCC who are being considered for liver transplant may be entered as a bridge to transplant if it is considered by the transplant team that an ablative therapy would be of value while awaiting transplant.
5. If cirrhosis is present, patients will have Child's-Pugh score of A or B (Appendix A).
6. Patients will have tumors not optimally treated with radio-frequency ablation by interventional radiology, or by GI/transplant surgery. This could be for reasons of size, tumor location, or other reasons.

7. Ability to place fiducial markers in the vicinity of the tumor to allow for radiographic tracking of respiratory motion and tumor localization. Fiducial placement will generally be done by interventional radiology.
8. Estimates of hepatic tolerance must meet the criteria as defined in Section 3.2 (Dose-Volume Constraints – Liver Tolerance Parameters)
9. Adequate bone marrow and renal function as assessed by the following:
 - Absolute neutrophil count (ANC) $\geq 1000/\text{mm}^3$
 - Platelet count $\geq 80,000/\text{mm}^3$
 - Creatinine $\leq 2.0 \text{ mg/dL}$ OR Creatinine clearance $\geq 45 \text{ mL/min}$ based on Cockcroft-Gault formula).
10. Patients with extrahepatic metastatic disease are eligible if it is the opinion of the treating physician that local therapy to the liver may produce worthwhile clinical benefits
11. Patient is able to understand fully the potential risks and benefits of this approach and signs an appropriate informed consent.
12. Male and female of >18 years of age. Male or female patients capable of reproduction must agree to use medically acceptable methods of contraception, such as an intra-uterine device, diaphragm, with spermicide, condom with spermicide or abstinence. Inclusion of females of childbearing potential requires a negative pregnancy test within 14 days prior to study initiation

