2.2 Secondary Objectives

To develop preliminary data on local response/control of HCC, colorectal liver metastases, and liver metastases from other primary sites to these radiation doses.

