5.0 EVALUATIONS AND ASSESSMENTS

5.1. Time and Events Table

Assessments	Pre-Study ^a	Cyberknife RT Delivery ^b	Post RT Week 1 ^h	Post RT Week 4	Post RT Week 8	Post RT Week 20	Follow-up q 3 Months ^c x 2 Years
Informed Consent	X						
History and PE	X	X		X	X	X	X
Performance Status	X			X	X	X	X
Chest x-ray	X						
CBC	X		X	X	X	X	
Liver function tests (T Bili, INR, PT for Child-Pugh score, AST, ALT, LDH, Alk Phosphatase, Albumin)		X		X	X	X	X
Serum Creatinine	X						
Circulating Tumor Markers : AFP (HCC) or CEA (CRC)	X				X	X	X
CT and/or MRI of liver, PET scan is optional	X				X	X	X
Fiducial Placement ^d	X						
Liver Biopsy (if needed for diagnosis confirmation)	X ^g						
Treatment Planning ^e	X						
Toxicity Assessment		X	X	X	X	X	X
Pregnancy Test	X ^g						

^a Pre-study assessments to be completed within 8 weeks prior to start of Cyberknife Radiation Therapy Treatment.

^bCyberKnife radiation therapy (RT) will be completed within 2 weeks depending on routine scheduling or maintenance related issues with the CyberKnife. No treatment should be completed in less than 5 days.

^c Every three months following week 20. See section 5.5 for additional details.

^dThis would be done after study entry but prior to radiation therapy (RT).

^eTo be done at least 6 days following fiducials placement. Participants will be immobilized using Vac-Loc and Synchrony vest to facilitate in obtaining the treatment planning CT.

^g Within 14 days pre-study, and only if clinically appropriate

^h Patients in whom high dose irradiation is delivered to the main hepatic ducts or common bile duct will be considered for elective stent placement within the first 4 weeks after completion of radiation therapy to prevent biliary obstruction.

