5.2 Pre-study Assessments

- Informed Consent
- History and physical examination
- Performance status
- Chest x-ray
- Laboratory studies including: CBC, LFT, Serum creatinine
- CT and/or MRI of the liver; PET scan is optional
- Pregnancy test within 14 days pre-study, and only if clinically appropriate

Fiducial placement: Prior to CT planning gold seed markers compliant with the CyberKnife software will be placed in the vicinity (within 6 cm) of the tumor as described in Section 3.2. CT planning in Radiation Oncology to be done at least 6 days after fiducial placement.

Liver biopsy: Tumor biopsies should occur pre-study (within 14 days of study entry), although earlier biopsies can be acceptable with the approval of the Principle Investigator (PI) if sufficient diagnostic information has been obtained. Tumor biopsies will be performed by qualified radiology/interventional radiology personnel under CT or US guidance (presumably at the time of fiducial placement) of the tumor site deemed least likely to produce patient discomfort or complications. Patients should be monitored per the site standard of care after the procedure and any complications graded and reported utilizing the criteria for toxicity reporting described in section 6. Up to three passes should be made if safe in the judgment of the physician performing the procedure. A 14-20 FG needle will be used, at the discretion of the interventional radiologist.

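### Inclusion 1 prints the AFP limit that, with imaging, can replace biopsy for HCC as 1000 ng/dL, which is 10 ng/mL; the value and unit need to be confirmed.

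*Combined protocol and SAP*

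**What the plan says.** Section 4.1, item 1, accepts HCC "as defined by biopsy or alpha-fetoprotein (AFP) greater than 1000ng/dL with appropriate imaging". The two routes are joined by *or*, so a patient with qualifying AFP and imaging needs no tissue.

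The biopsy provisions elsewhere leave that route open. The row in the Time and Events Table (section 5.1) reads "Liver Biopsy (if needed for diagnosis confirmation", which makes biopsy conditional. Section 5.2 says "Tumor biopsies should occur pre-study (within 14 days of study entry), although earlier biopsies can be acceptable". That sentence governs timing and does not withdraw the AFP alternative.

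Section 5.1 also lists AFP as a study measurement for HCC, without a unit. No section gives a second AFP limit, an assay reference range or a source for the figure of 1000. The imaging that must accompany AFP is not described further.

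The HCC label matters for the secondary objective in section 2.2: "To develop preliminary data on local response/control of HCC, colorectal liver metastases, and liver metastases from other primary sites".

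**The concern.** A marker limit that can replace tissue helps decide who has the disease under study, so its unit has to be right. The printed denominator is the decilitre, which makes the limit 100 times lower than the same numeral per millilitre. Decilitres are also used for creatinine in item 9 of the same list and for bilirubin and albumin in Appendix A, so the unit could easily have carried over.

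Two things are at stake.

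- **Consistency of eligibility.** If laboratories report AFP in ng/mL (an assumption; the documents are silent), a reader who converts applies 10 ng/mL, and a reader who compares only the numeral applies 1000 ng/mL. An unbiopsied patient between the two is eligible under one reading and not under the other.
- **The local-control result.** Read literally, the criterion could admit a lesion that is not HCC, provided it also passes the imaging requirement. Section 5.6.1 calls an irradiated lesion progressive only when the product of its two perpendicular diameters rises by 50% or more, and section 5.6 takes the week-8 scan as baseline. A lesion that does not grow that much would be scored as controlled, whatever it was.

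**Working it through.** The limit is an input to the plan and not a derived figure, so there is no calculation of the sponsor's to reproduce. The check is a unit conversion, followed by its possible effect on one dose level.

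**Inputs**

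- AFP limit: above 1000 ng/dL (section 4.1, item 1).
- Patients per dose level: 10 (Table 2; section 7.2).
- Local-control goal: at least 70% (sections 3.2 and 7.1).
- Escalation trigger: 4 local failures in a cohort at dose level 1, if toxicity is acceptable (sections 3.2 and 7.1).
- Assumption: a lesion counts as controlled if it is not progressive under section 5.6.1.

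**Step 1: convert the printed limit.** 1 dL = 100 mL, so 1000 ng/dL ÷ 100 mL/dL = 10 ng/mL.

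**Step 2: compare with the same numeral per millilitre.** 1000 ng/mL × 100 mL/dL = 100,000 ng/dL. The ratio is 10 ÷ 1000 = 0.01, so the printed limit is 1/100 of 1000 ng/mL.

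**Step 3: who is affected.** Only unbiopsied HCC patients with AFP above 10 and up to 1000 ng/mL. The documents give no way to estimate how many there are.

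**Step 4: effect on one dose level.** The level has 10 places, so a lesion that is not HCC takes the place of a true tumour. The result changes only if that tumour would have failed.

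| Level of 10 | Controlled | Failures | 70% goal | Four-failure trigger |
|---|---|---|---|---|
| Ten true tumours, four fail | 6/10 = 60% | 4 | missed | met |
| One failing tumour replaced by a lesion that does not grow | 7/10 = 70% | 3 | met | not met |

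Section 7.2 words the trigger as a failure rate above 30%. That gives the same split: 4/10 = 40% exceeds 30%, and 3/10 = 30% does not.

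**Step 5: how often this could matter.** Assume independent failures with probability *p* per true tumour. Compare P(at least 4 failures) for ten true tumours with the same probability for nine true tumours plus one lesion that cannot fail. The difference is *p* × P(exactly 3 of 9 fail). The documents give no *p*, so a range is shown.

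| Assumed *p* | Ten true tumours | Nine plus one | Difference |
|---|---|---|---|
| 0.30 | 0.350 | 0.270 | 0.080 |
| 0.40 | 0.618 | 0.517 | 0.100 |
| 0.50 | 0.828 | 0.746 | 0.082 |

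One such lesion in a level therefore lowers the chance of reaching the trigger by about 8 to 10 percentage points over this range.

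**The case against.** The strongest reply is that the documents contain no contradiction. Only one AFP limit is printed, and nothing in the plan conflicts with it. This stands: a reader might infer that 1000 ng/mL was certainly intended, or that 10 ng/mL is close to normal and so cannot identify HCC, but the documents give neither a reference range nor a source that would establish either.

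Second, AFP alone admits nobody. Imaging is required as well, and items 3 and 6 of section 4.1 add that the patient is not a candidate for definitive resection and that the tumour is not optimally treated by radiofrequency ablation. This also stands. It makes a wrongly labelled lesion less likely, but the imaging requirement has no stated content and does not fix the unit.

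Third, registration runs through one centre, and affiliates send in eligibility documents (section 8.2), so sites may not in fact diverge. That is fair. A 100-fold difference is what the wording permits, not something shown to have happened. Anyone who reads only the numeral would be applying the stricter limit.

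Fourth, a reader might compare 6 of 9 with 7 of 10 and conclude that simply adding one benign lesion blocks escalation. The plan does not support that: both contain three failures, so the count of four is unmet either way, and each level plans 10 patients. The valid comparison is replacement within ten, as in Step 4.

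Finally, each dose level pools HCC with metastases, and local control is a secondary endpoint described as preliminary. This limits the reach of the point but does not remove it.

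**Conclusion.** The point holds in a limited form. As printed, the AFP limit that can replace biopsy is 10 ng/mL, and it is uncorrected and unexplained. That the unit is a slip is probable but unproven.

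The effect falls on diagnostic certainty and on the unbiopsied HCC part of the local-control objective. One lesion that is not HCC could move a level of 10 from missing the 70% goal to meeting it, and from reaching the four-failure trigger to not reaching it. This requires that the lesion passed the imaging requirement, did not grow by 50% or more from week 8, and took the place of a tumour that would have failed. How many patients this could involve is unknown.

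A reader might go on to infer that the trial's primary result is undermined. The documents do not support this: the definition of dose-limiting hepatic toxicity, the stopping rules in Tables 3 and 4 and the sample size in section 7.2 make no use of AFP.

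**What to change.** The sponsor should confirm the intended AFP value and unit, state the basis, and correct section 4.1, item 1, accordingly, in the unit that the participating laboratories report. This review does not name the limit. Saying what imaging qualifies would close the remaining gap in the same sentence.

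For any patient already enrolled on AFP without biopsy, list the AFP value in that unit, and report HCC local control with and without those who do not meet the confirmed limit.

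The cost is a minor amendment and a short listing. Depending on the confirmed limit, some patients may need the biopsy route that the protocol already provides.

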4.2 Exclusion Criteria

1. Child-Pugh Class C cirrhosis
2. Patients with clinically apparent CNS disease.
3. Medical or psychiatric illness that would not allow the patient to tolerate the proposed treatment including inability to lie flat for an extended period of time, severe claustrophobia or other reasons.
4. Uncontrolled or significant cardiovascular disease including: myocardial infarction within 6 months, uncontrolled angina within 6 months, Class III-IV New York Heart Association (NYHA) congestive heart failure, grade 3 cardiac valve dysfunction.
5. Evidence of decompensated liver disease as evidenced by: clinically significant ascites (refractory to diuretic therapy), evidence of hepatic encephalopathy, coagulopathy not corrected by conservative measures.
6. A history of CTCAE Grade 3 bleeding esophageal or gastric varices within the past 2 months. Prior variceal bleed permitted if patient has undergone banding or sclerotherapy and there has been no evidence of bleeding for 2 months. Patients at risk for varices (based on the following: known history of esophageal or gastric varices; evidence of hepatic cirrhosis and/or portal hypertension including biopsy-proven cirrhosis, hypersplenism, or radiographic findings of varices) will be screened for esophageal varices. If varices are identified that require intervention (banding), patient will not be eligible until varices adequately treated.
7. Prisoners or patients who are compulsorily detained (involuntarily incarcerated) for treatment of either a psychiatric or physical (e.g., infectious disease) illness must not be enrolled into this study.
8. Uncontrolled intercurrent illness.

9. Inability to comply with study and/or follow-up procedures.

10. A patient with Child-Pugh Class A will not be eligible for study if the liver dose constraint described in Section 3.2 cannot be met after two decrements in dose per fraction as described above.

11. A patient with Child-Pugh Class B will not be eligible for study if the liver dose constraint described in Section 3.2 cannot be met after two decrements in dose per fraction as described above.

5.0 EVALUATIONS AND ASSESSMENTS

5.1. Time and Events Table

Assessments	Pre-Study ^a	Cyberknife RT Delivery ^b	Post RT Week 1 ^h	Post RT Week 4	Post RT Week 8	Post RT Week 20	Follow-up q 3 Months ^c x 2 Years
Informed Consent	X						
History and PE	X	X		X	X	X	X
Performance Status	X			X	X	X	X
Chest x-ray	X						
CBC	X		X	X	X	X	
Liver function tests (T Bili, INR, PT for Child-Pugh score, AST, ALT, LDH, Alk Phosphatase, Albumin)		X		X	X	X	X
Serum Creatinine	X						
Circulating Tumor Markers : AFP (HCC) or CEA (CRC)	X				X	X	X
CT and/or MRI of liver, PET scan is optional	X				X	X	X
Fiducial Placement ^d	X						
Liver Biopsy (if needed for diagnosis confirmation)	X ^g						
Treatment Planning ^e	X						
Toxicity Assessment		X	X	X	X	X	X
Pregnancy Test	X ^g						

^a Pre-study assessments to be completed within 8 weeks prior to start of Cyberknife Radiation Therapy Treatment.

^bCyberKnife radiation therapy (RT) will be completed within 2 weeks depending on routine scheduling or maintenance related issues with the CyberKnife. No treatment should be completed in less than 5 days.

^c Every three months following week 20. See section 5.5 for additional details.

^dThis would be done after study entry but prior to radiation therapy (RT).

^eTo be done at least 6 days following fiducials placement. Participants will be immobilized using Vac-Loc and Synchrony vest to facilitate in obtaining the treatment planning CT.

^g Within 14 days pre-study, and only if clinically appropriate

^h Patients in whom high dose irradiation is delivered to the main hepatic ducts or common bile duct will be considered for elective stent placement within the first 4 weeks after completion of radiation therapy to prevent biliary obstruction.

5.2 Pre-study Assessments

- Informed Consent
- History and physical examination
- Performance status
- Chest x-ray
- Laboratory studies including: CBC, LFT, Serum creatinine
- CT and/or MRI of the liver; PET scan is optional
- Pregnancy test within 14 days pre-study, and only if clinically appropriate

Fiducial placement: Prior to CT planning gold seed markers compliant with the CyberKnife software will be placed in the vicinity (within 6 cm) of the tumor as described in Section 3.2. CT planning in Radiation Oncology to be done at least 6 days after fiducial placement.

Liver biopsy: Tumor biopsies should occur pre-study (within 14 days of study entry), although earlier biopsies can be acceptable with the approval of the Principle Investigator (PI) if sufficient diagnostic information has been obtained. Tumor biopsies will be performed by qualified radiology/interventional radiology personnel under CT or US guidance (presumably at the time of fiducial placement) of the tumor site deemed least likely to produce patient discomfort or complications. Patients should be monitored per the site standard of care after the procedure and any complications graded and reported utilizing the criteria for toxicity reporting described in section 6. Up to three passes should be made if safe in the judgment of the physician performing the procedure. A 14-20 FG needle will be used, at the discretion of the interventional radiologist.

5.3 Treatment Assessments

- Toxicity Assessment
- Physical examination and history

5.4 Post-treatment Assessments (Up to week 20 after RT Treatment)

- History and physical examination
- Performance status
- Laboratory studies including CBC, and liver function tests
- CT, PET or MRI of the liver will be performed at, 8 and 20 weeks after the completion of radiation therapy and then at regular intervals per Section 5.1.
- Toxicity assessment (NOTE: this should occur up to week 20 regardless of whether disease recurs prior to this point or not).

5.5 Follow-up Assessments:

Follow-up will be done every three months for two years, or until disease progresses in an irradiated liver lesion. If disease progresses in a non-irradiated lesion only, follow-up will continue until disease progresses in one of the irradiated liver lesions. Once disease progresses in an irradiated liver lesion, protocol follow-up will cease other than follow-up of any unresolved treatment-related toxicity. Follow-up assessments will include:

- History and physical examination
- Performance status
- Laboratory studies for liver function tests
- CT, PET or MRI of the liver.
- Toxicity assessment

Patients in whom high dose irradiation is delivered to the main hepatic ducts or common bile duct will be considered for elective stent placement within the first 4 weeks after completion of radiation therapy to prevent biliary obstruction.

5.6 Assessment of Disease Status

Criteria for response evaluation in patients with measurable disease:

Patients eligible for this trial must have at least one measurable liver lesion and no more than 3 liver lesions. Any of these measurable liver lesions irradiated under this protocol will be separately evaluated for progression/response. These measurable irradiated lesions must be accurately measured in at least two dimensions.

Progression in any non-irradiated liver lesion or distant site (including non-measurable disease e.g., ascites, malignant pleural/pericardial effusion, bone lesions, or marrow involvement) will be evaluated separately. These non-irradiated lesions will be followed up for progression only.

It is a known and expected effect from radiosurgery for there to be peri-lesional enhancement up to 2.5 cm surrounding the target lesion that will not be considered as part of the response criteria or as tumor progression. Therefore, specifically for the irradiated liver lesions, the 8 weeks post treatment tumor assessment will be considered baseline for evaluation of progression/response.

